STUDY PROTOCOL

EFFICACY OF PC6 ELECTROACUPUNCTURE IN THE PREVENTION OF NAUSEA VOMITING IN CAESAREAN PATIENT UNDER SPINAL ANAESTHESIA

NMRR ID: 19-3279-51524(IIR)

Date: 4th MARCH 2020

Sponsor: Self-sponsored study

Institution:

Hospital Raja Permaisuri Bainun Ipoh

Sampling Method

Potential study subject is identified when booking for elective is made to the Maternal Operating Theatre. Upon identification of potential subject, the patient shall be seen by the anaesthetic doctor in the ward for recruitment purposes a day before the operation (patient scheduled for elective LSCS will be admitted a day before in maternal ward and will be seen by anaesthetist in the ward a day before). The patient is then further assessed by investigators for suitability for recruitment into the study, and if the patient fulfils the criterion, patient is then counselled for enrolment into the study. Patient will be informed on the study objectives, electroacupuncture and its potential side effects including minimal discomfort over the puncture site, redness after removal of needle. They will also be informed that randomization will take place and that they may receive granisetron and sham acupuncture or electroacupuncture and granisetron.

Subsequently, assessment for data collection will also be explained to them i.e. nausea and vomiting assessment. The subject will be informed regarding circumstances where they will be excluded or withdrawn from the study. Upon agreement for enrolment, informed consent form will be provided to the patient and explained in detail the process of randomisation, study procedure including procedures for provision of spinal anesthesia, method of assessment postoperatively, as well as the potential side effects of electroacupuncture before they sign and date on the informed consent form. Once the patient agreed to get enrolled, she will be consented a day before the operation.

When the patient is successfully enrolled, by using simple randomization they will be assigned to one of two groups (EA or sham group) using sealed envelope method. Sham group

shall receive 1mg of IV granisetron and sham acupuncture while the EA group shall receive 1mg of IV granisetron and electroacupuncture throughout the surgery.

The identity of the envelop shall only be known by an independent assisting nurse and acupuncture performer (In this study, principal investigator will be the acupuncture performer).

Study protocol

All patients scheduled to have surgery will be approached and given time to read the information sheet and entered into the study after signing the consent form a day before the operation in maternal ward.

Subarachnoid puncture in the L3-L4 or L4-L5 interspace will be performed by an anesthesiologist with the patients in the sitting position, using a 27 gauge sprotte spinal needle. Patients will receive dosage of heavy Marcaine 0.5% range from 1.8-2.2ml according to patient height (figure3), fentanyl 15mcg, morphine 0.1mg, in order to achieve T4-T6 sensory blockade. Then the patients will be repositioned into supine position. The level of anesthesia will be evaluated. In order to prevent inferior vena cava syndrome (supine hypotension syndrome) the beds will be rotated 15⁰ to the left. Patients will receive 3 l/min of oxygen by nasal canula. Non-invasive blood pressure measurement will be performed every 2 minutes until the patient left the operating room. A decrease in systolic blood pressure (>25% decrease or BP<90 mmHg) will be treated with 100 mcg intravenous phenylephrine or 6mg ephedrine. A decline in pulse rates (<50 beats per min) will be treated with 0.5 mg intravenous atropine.

141cm-150cm	1.8ml-2.0ml
-------------	-------------

151cm-160cm	2.0ml-2.1ml
161cm-170cm	2.2ml-2.3ml
>170cm	2.3ml

Table 1. Dosage of 0.5% heavy bupivacaine according to patient's height

Patients in the EA group will have the acupuncture needles inserted at bilateral Pericardium Meridian point 6 (PC6) and large intestine meridian point 4 (LI4) (Figure 1) after given spinal anaesthesia and in supine position.

The pericardium meridian PC6 point (Neiguan) is defined as follows. The patient's four fingerbreadths will be placed on the medial aspect of their forearm with the edge of the 4th finger on the wrist crease. This is then subtracted from the width of the interphalangeal joint of her thumb. The point between the tendons of extensor carpi radialis and palmaris longus was the pericardium meridian PC6 point (Neiguan) (Figure 1). The large intestine LI4 point (Hegu) located on the dorsum of the hand, between the first and second metacarpal bones, at the midpoint of the second metacarpal bone and close to its radial border (Figure 1).

In this study, principal investigator is a trained acupuncture performer and given privilege to perform acupuncture procedure in Hospital Raja Permaisuri Bainun ever since she was trained in Guangzhou (A programme organized by kementerian

Kesihatan in 2011). The principal investigator will be responsible for locating and demarcating the correct acupoint. The needles will be inserted by using a “flicking in” technique with a needling guide tube to ensure it is at an appropriate depth (0.5-1 cun). The EA needles will be stimulated before the start of surgery until the end of surgery at a frequency of 2 Hertz that will be produced by Electronic Acupuncture Treatment. It will be set at intensity level 1 with continuous wave emission. This device uses alternating current (AC) for a substantial step-down in voltage and amperage and ensured that there will be virtually no current transmitted through the patient’s body for intraoperative safety. The proximal and distal electrodes will be clipped on to the sterile single use acupuncture needles. Stimulation was stopped and needles removed at end of surgery.

In sham/placebo group, patient will have the acupuncture needles inserted at non-acupoint 2cm radial to PC6 and between 2nd and 3rd metacarpal bone bilaterally as shown in the figure 6, superficial skin piercing (adequate depth to let patient feels needle is inserted). After the acupuncture needles are inserted, it will be attached to the electronic acupuncture electrode but without stimulation. To facilitate blinding, the machine is placed caudal to the patient, patient is unaware of the machine on/off but patient will be able to observe the procedure (needle insertion) being performed on both hands.

[figure not shown]

Figure 1

Position of electrodes: (figure 2)

The proximal and distal electrodes have to be on opposite sides for both arms. Eg:

Right hand: PC6...yellow, LI4: red, Left hand: PC6...red, LI4: yellow

Figure 3: position of electrodes

Figure 4: Sham acupoints

After the CS is implemented, the patient will be brought to the recovery room, and left there after regaining the sensory level of T10 (umbilical level) with a stable situation. Nausea and vomiting during the surgery or in the recovery room will be treated with 10 mg i.v. metoclopramide (usual treatment dose for nausea and vomiting) The data regarding the occurrence of nausea or vomiting within the theatre or recovery rooms were written in the checklists by the anesthesiology technician. PONV was observed at the ward by the nurses up to 24 hours post operation. Nausea and vomiting in ward will be prescribed with IV metoclopramide 10mg(0-6 hours post operation), and IV granisetron 1mg (> 6 hours post operation). The patients' charts were assessed at the end of 24 hours for anti-emetic requirements.

The postoperative analgesia regimen is standardized, rectal diclofenac 100mg will be given at the end of the surgery and continue with tablets paracetamol 1g 4 times per day and tablets diclofenac acid 50mg 3 times per day.

In this study, even though the principle investigator is a subspecialized obstetric anaesthesiologist given privilege to perform acupuncture, she will perform all the acupuncture procedure only, she will be independent and will not interfere with any of the anesthesiology clinical decision made on the subject.

There will be no cessation of medication if patient is on any or medication not permitted in this study. But those drugs which known to affect nausea vomiting and have to be given to the patient to ensure patient comfort (antiemetic, opioid usage) preoperatively or intraoperatively, patient will be excluded from the study (inclusion, exclusion and withdrawal criterion)

Safety monitoring of subjects- Patient's vital signs will be monitored once patient is given spinal anesthesia including continuous electrocardiography, continuous heart rate, continuous oxygenation saturation, non-invasive blood pressure every 2 minutes, patient is awake and able to communicate with investigators throughout the whole surgery, pain at needle insertion site will be monitored time to time. Needle will be removed once operation is done. Post operatively, patient will be observed in the ward for 24hours. Other than that, fetal heart rate will be monitored using doppler fetal monitor before and after acupuncture is performed.

Adverse effect and management- As the puncture site is safe (over the hand, away from main vessels) and the needle is tiny, it can rarely cause serious adverse event. The most serious event will be syncopal which happens in needle phobia patient (who will be not be included in the study during recruitment) and interference with pacemaker (exclusion criteria in this study), the most common drawback of the

acupuncture practice couple using electroacupuncture machine will be pain and hematoma at the needle insertion site but is usually transient and self-limiting. Furthermore it is done in a controlled environment (operation theatre) with resuscitation equipment and experience personnel further ensure the safety of subjects. In the cases of study related injury, patient will receive necessary treatment in Hospital Raja Permaisuri Bainun until recover.

Sample Size

Objective 1:

For this study, it is expected the incidence of IONV in granisteron group to be 52%, whereas for electroacupuncture and granisetron group, 22%.

Power and Sample size Program, ScalexProp version 1.0.2 (Naing, 2016) is used to estimate the sample size for this objective. It is planned that this study consists of independent cases and controls with 1 control(s) per case. Prior data indicate that the failure rate among controls is 0.52. If the true failure rate for experimental subject is 0.22, 37 experimental (electroacupuncture+granisetron) subjects and 37 control (granisetron alone) subjects will be needed to be able to reject the null hypothesis that the failure rates for experimental and control subjects are equal with probability (power) 0.8. The Type I error probability associated with this test of this null hypothesis is 0.05.

Including 20% potential drop out rate, the sample size needed for this study is 88 patients (44 for electroacupuncture+granisetron arm and 44 for granisetron arm).

Objective 2:

No prior research was done using a recommended dose 1mg of granisetron in cesarean section patient for reduction in incidence of PONV up to 24 hours. However there is a RCT done in 2017 by Chang Yen Yin et al comparing the efficacy of acupuncture plus ondansetron versus ondansetron after bupivacaine-morphine spinal anesthesia, this study showed that the incidence of PONV up to 24 hours were 43% in ondansetron group versus 16% in acupuncture plus ondansetron. Since most of the literature stated the 5HT3 antagonist drugs (4mg IV ondansetron and 1mg IV granisetron) have similar efficacy to prevent PONV.

For this study, it is expected that the incidence of PONV in granisetron group to be 43%, whereas for electroacupuncture and granisetron group, 16%.

Power and Sample size Program, ScalexProp version 1.0.2 (Naing, 2016) is used to estimate the sample size for this objective. We are planning a study of independent cases and controls with 1 control(s) per case. Prior data indicate that the failure rate among controls is 0.43. If the true failure rate for experimental subject is 0.16, we will need to study 41 experimental (electroacupuncture+granisetron) subjects and 41 control (granisetron alone) subjects to be able to reject the null hypothesis that the failure rates for experimental and control subjects are equal with probability (power) 0.8. The Type I error probability associated with this test of this null hypothesis is 0.05.

Including 20% potential drop out rate, the sample size needed for this study is 98 patients (49 for electroacupuncture+granisetron arm and 49 for granisetron arm).

Data Collection

Postoperative data collection shall be done by trained APS team. The details to be filled in the form include patient general demographic data (Age, gender, weight), anaesthetic regime (dosage of heavy bupivacaine 0.5%), indication of caesarean section (breech presentation, one previous scar refuse vaginal birth), intraoperative exteriorization of uterus, as well as duration of surgery in minutes.

Nausea and vomiting are then assessed intraoperatively in operating theatres and post operatively in recovery room and ward. Retrospective assessment will be done by study team in ward to assess nausea and vomiting incidence at 0-12 Hrs post operation and 12-24 hrs post operation.

Pain score will be assessed as well using the numeric rating scale. The Numeric Rating Scale is a well-established tool in pain measurement. The presence of nausea and vomiting will be assessed using a four-point scale adapted from a study done by Y Fuji et al.

The scale used was:

- I. None
- II. Nausea only

III. vomiting/retching only

IV. Nausea and vomiting/retching

Study Instruments

1. Sterile acupuncture needles for single use.

2. Electroacupuncture machine

(Medical Device Authority registration number: GB82707425017)

Validity Date of Registration 13/11/2017-12/11/2022

Electronic acupuncture treatment device uses low frequency pulse to stimulate the acupoints of human body.

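### In theatre, only the patient is shielded from the cues that separate the arms; no stated measure shields the technician who records intraoperative nausea and vomiting

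*Protocol*

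**What the plan says.** All references are to the protocol.

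- **Who may know the arm** (Sampling Method): "The identity of the envelop shall only be known by an independent assisting nurse and acupuncture performer". The technician is not on that list, so the intent is that the technician does not know.
- **Electroacupuncture (EA) arm** (Study protocol): "acupuncture needles inserted at bilateral Pericardium Meridian point 6 (PC6) and large intestine meridian point 4 (LI4"), with a "needling guide tube to ensure it is at an appropriate depth (0.5-1 cun"). The needles are stimulated at 2 Hz from before the start of surgery until its end.
- **Sham arm** (Study protocol): needles "inserted at non-acupoint 2cm radial to PC6 and between 2nd and 3rd metacarpal bone bilaterally", by "superficial skin piercing (adequate depth to let patient feels needle is inserted"). Electrodes are attached but no current is delivered.
- **Concealment of the machine's state** (Study protocol): "To facilitate blinding, the machine is placed caudal to the patient, patient is unaware of the machine on/off". The same sentence adds that the "patient will be able to observe the procedure (needle insertion) being performed on both hands".
- **Who records** (Study protocol): nausea or vomiting occurring "within the theatre or recovery rooms were written in the checklists by the anesthesiology technician". Nothing is said about whether this person is blinded or screened.
- **Scale** (Data Collection): four categories, three of them positive, one of which is nausea alone.
- **Later checks**: charts are reviewed at 24 hours for anti-emetic use (Study protocol), and the study team assesses the 0-12 and 12-24 hour windows retrospectively in the ward (Data Collection).

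**The concern.** The envelope rule controls who is told the arm. It does not control who can see it. While IONV is being recorded, three cues are present: a different metacarpal space and a forearm point 2 cm away, a different needle depth, and a device that is either running or idle. The step that hides the last of these protects the patient's view only.

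This matters most for IONV because it is Objective 1 and because nausea alone has no outward sign that a third party can verify. Someone has to ask, hear the answer and write it down. If knowledge of the arm made the recorder slightly less ready to note an event in EA patients, the shortfall would look like a treatment effect, and no later analysis could recover events that were never written down.

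**Working it through.** **1. The protocol's own figure.** Objective 1 assumes 52% IONV with granisetron alone and 22% with electroacupuncture added, power 0.80 and alpha 0.05 (taken as two-sided; the protocol does not say). The unpooled formula gives

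n = (1.960 + 0.842)² × [0.52×0.48 + 0.22×0.78] / (0.52 − 0.22)² = 36.7, rounded up to 37 per arm.

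This matches the protocol, as does 37 × 1.2 = 44.4 against its 44 per arm after the dropout allowance. The inputs are therefore read correctly.

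**2. Cues against safeguards in theatre.**

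| Cue | EA arm | Sham arm | Hidden from patient? | Stated measure hiding it from technician? |
|---|---|---|---|---|
| Site | PC6 and LI4 | 2 cm radial to PC6; 2nd-3rd metacarpal space | No; needling stays visible by design | None |
| Depth | 0.5-1 cun | Superficial | No specific measure | None |
| Machine state | 2 Hz | Off | Yes, by position | None |

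**3. Sensitivity to missed events.** The protocol gives no miss rate, so every value of m below is an assumption. Suppose there is no true effect, the true rate is 0.52 in both arms, and a fraction m of EA events goes unrecorded. The recorded EA rate is then 0.52(1 − m). For a two-sided pooled z-test:

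- d = 0.52m, and p̄ is the mean of the two recorded rates
- s₀ = √[2p̄(1 − p̄)/n]; s₁ = √{[p₁(1 − p₁) + p₂(1 − p₂)]/n}
- P(significant in favour of EA) = Φ[(d − 1.96 s₀)/s₁]
- P(significant against EA) = Φ[(−d − 1.96 s₀)/s₁]

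Example, n = 37 and m = 0.10: p₂ = 0.468, d = 0.052, p̄ = 0.494, s₀ = 0.1162, s₁ = 0.1161. In favour: Φ(−1.515) = 0.065. Against: Φ(−2.411) = 0.008. Total 0.073.

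| m | EA events missed at n = 37 (of 37×0.52 = 19.2) | Two-sided, n = 37 | In favour of EA, n = 37 | Two-sided, n = 44 |
|---|---|---|---|---|
| 0 | 0 | 5.0% | 2.5% | 5.0% |
| 0.05 | 1.0 | 5.6% | 4.1% | 5.7% |
| 0.10 | 1.9 | 7.3% | 6.5% | 7.7% |
| 0.20 | 3.8 | 14.5% | 14.2% | 16.3% |

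Exact binomial enumeration at 37 per arm gives 4.7%, 5.3%, 7.0% and 14.0% for the two-sided column, so the approximation is adequate.

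**4. A narrower case.** If only nausea-alone events can be missed, and 20% of them are, the two-sided rate at 37 per arm is 6.0%, 7.3% or 9.1% when such events make up one third, half or two thirds of all events. Those shares are also assumed.

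**The case against.** The defence has real substance.

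- **The arms are made to look alike.** Both have needles in hands and forearms and the same electrodes attached, and the machine is at the caudal end. The protocol does not say where the technician stands, whether the technician can tell a real point from a sham one, or whether the on/off state can be seen. This stands: access to the arm is possible, not shown.
- **The bias path is narrow.** The patient who feels the nausea is awake and blinded. Vomiting and retching can be observed. The protocol says nausea and vomiting in surgery will be treated, so recognised events should leave a drug record. This also stands. What remains is nausea that is neither written down nor treated, in one arm more than the other.
- **Recovery is different from theatre.** The needles are out and stimulation has ended. Only knowledge carried over by the same technician role is at issue, and the study team's retrospective 0-12 hour assessment is a second check, although that team's blinding is not stated. A reader might infer that recovery and ward outcomes are equally exposed; the documents do not support that.
- **The treating anaesthetist.** A reader might extend the point to this person, but the protocol does not show the anaesthetist recording outcomes. Blinding that role is desirable, not essential to this point.
- **Incomplete text.** The available protocol begins at Sampling Method and refers to eligibility and withdrawal criteria that are not shown. A safeguard could stand elsewhere, which lowers confidence.

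None of this supplies a measure that keeps the cues from the in-theatre recorder. Limiting who knows the envelope does not do so.

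**Conclusion.** The point holds for IONV in theatre. The protocol means the technician not to know the arm, but it gives practical protection only to the patient. Recovery is a lesser concern.

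The tempting stronger reading is that IONV will be recorded unblinded and the Objective 1 result will be biased. The documents do not support it: they are silent on what the technician sees, and they give no miss rate. The calculations show sensitivity, not likely bias. They assume misses in the EA arm only and a two-sided test. Missing one EA event in about 19 is negligible (5.6%), two gives about 7.3%, and about four gives 14.5%, nearly all of it in favour of EA.

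The change is worth making because the affected outcome is Objective 1 and the remedy is cheap. The point does not invalidate the design. Confidence is medium.

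**What to change.** Add to the Study protocol section, where the sham procedure and outcome recording are described:

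1. The technician who records nausea and vomiting is blinded to allocation and is not present at the needling.
2. After insertion, which stays visible to the patient, the acupuncture performer or the assisting nurse covers both hands and forearms and screens the machine from the technician until the needles are removed.
3. Neither of these two unblinded persons records nausea or vomiting.

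**Cost:** drapes, a screen for the machine and two or three sentences of text. The main drawback is that any visual check of a needle site, for example if the patient reports pain there, means briefly uncovering it out of the technician's view. One of the two already-unblinded persons must therefore be reachable throughout surgery; the protocol does not currently say that either stays, so this needs to be arranged.

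### The protocol excludes patients who need an antiemetic or opioid during surgery, which is after randomisation and can depend on the Objective 1 outcome

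*Protocol*

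**What the plan says.** All places are in the protocol; no SAP is at hand.

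- **Exclusion.** In the section headed Study protocol, the paragraph on medication opens with "There will be no cessation of medication if patient is on any or medication not permitted in this study". It then turns to drugs known to affect nausea and vomiting that must be given for the patient's comfort: "antiemetic, opioid usage) preoperatively or intraoperatively, patient will be excluded from the study". It refers the reader to the inclusion, exclusion and withdrawal criteria, which are not in the text available.
- **Rescue.** Earlier in the same section: "Nausea and vomiting during the surgery or in the recovery room will be treated with 10 mg i.v. metoclopramide".
- **Drugs given to everyone.** Both arms receive granisetron (Sampling Method), and the spinal anaesthetic contains "fentanyl 15mcg, morphine 0.1mg, in order to achieve T4-T6 sensory blockade" (Study protocol).
- **Timing.** Under Sampling Method: "Once the patient agreed to get enrolled, she will be consented a day before the operation", and then "When the patient is successfully enrolled, by using simple randomization they will be assigned to one of two groups". Under Study protocol: "The EA needles will be stimulated before the start of surgery until the end of surgery".
- **Status after exclusion.** Sampling Method says that patients are told of "circumstances where they will be excluded or withdrawn from the study". It does not say what follows for data collection.

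**The concern.** A patient can be removed from the comparison after she has been randomised and after stimulation has started. The trigger, needing an antiemetic or opioid during surgery, is closely related to what Objective 1 measures and to what EA is meant to change. Selecting patients on such an event breaks the balance that randomisation provides.

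Losing IONV cases from the control arm makes EA look less effective; losing them from the EA arm makes it look more effective. If exclusion also ends follow-up, the 24-hour postoperative nausea and vomiting (PONV) data for Objective 2 are lost as well, and no analysis plan can recover them.

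The wording also leaves the scope open. Metoclopramide given for nausea during surgery is an antiemetic given intraoperatively for comfort. Staff who apply the sentence as written could remove patients because they had the Objective 1 event.

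**Working it through.** **1. When the exclusion falls.** Consent is taken the day before surgery, randomisation follows enrolment, and stimulation begins before surgery starts. Any intraoperative exclusion is therefore later than both randomisation and the start of treatment. Some preoperative exclusions may also come after randomisation, but the protocol gives no time for opening the envelope, so that part is only possible.

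**2. The protocol's own sample size.** Inputs: IONV 52% versus 22% (Sample Size, Objective 1); PONV 43% versus 16% and 49 per arm after the 20% allowance (Sample Size, Objective 2); alpha 0.05, taken as two-sided; power 0.80. The unpooled formula is n = (1.960 + 0.842)² × [p₁(1−p₁) + p₂(1−p₂)] / (p₁−p₂)².

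- Objective 1: 7.849 × (0.2496 + 0.1716) / 0.09 = 36.7, so 37 as stated.
- Objective 2: 7.849 × (0.2451 + 0.1344) / 0.0729 = 40.9, so 41 as stated.

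The same unpooled approach is used for power below.

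**3. Narrow reading: only drugs outside the protocol lead to exclusion.** With 49 per arm, the expected IONV cases are 49 × 0.52 = 25.48 (control) and 49 × 0.22 = 10.78 (EA). The number excluded is not given, so the calculation is per excluded IONV case. The figure of three is an assumption.

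| IONV cases excluded | Control rate | EA rate | Risk difference (points) | Odds ratio |
|---|---|---|---|---|
| None | 52.0% | 22.0% | 30.0 | 0.26 |
| 1 control | 24.48/48 = 51.0% | 22.0% | 29.0 | – |
| 1 EA | 52.0% | 9.78/48 = 20.4% | 31.6 | – |
| 3 control | 22.48/46 = 48.9% | 22.0% | 26.9 | 0.30 |
| 3 EA | 52.0% | 7.78/46 = 16.9% | 35.1 | 0.19 |

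The effect is larger for EA patients because that arm has fewer events.

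**4. Only if the rule were applied to rescue.**

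- *Upper bound, every IONV case rescued and excluded.* About 25 controls and 11 EA patients are lost. The overall loss is (0.52 + 0.22)/2 = 37%, against the 20% allowed for drop-out, and no IONV event remains to analyse.
- *Half of the IONV cases in each arm excluded (assumption).* The observed rate becomes p(1 − 0.5)/(1 − 0.5p), which is 0.26/0.74 = 35.1% and 0.11/0.89 = 12.4%. The arms shrink to 49 × 0.74 = 36.3 and 49 × 0.89 = 43.6. The standard error is √(0.351 × 0.649/36.3 + 0.124 × 0.876/43.6) = 0.0936, so z = 0.228/0.0936 = 2.43 and power is Φ(2.43 − 1.96) = 0.68.
- *No exclusion.* The standard error is √(0.4212/49) = 0.0927, z = 3.24 and power is 0.90.

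**The case against.** The strongest reply is that the rule cannot cover drugs the protocol itself prescribes. Every patient receives granisetron and spinal opioids, so a fully literal reading would exclude everyone. The paragraph is about medication that is not permitted, whereas metoclopramide is named in the same section as the treatment for intraoperative nausea. The protocol also records nausea and vomiting in theatre and reviews charts for antiemetic requirements at 24 hours, which makes little sense if rescued patients have left the study. The criteria list that the sentence points to is not visible and may settle the scope. Analysis populations are normally left to the SAP.

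Much of this stands. The narrow reading is the more likely one, and the figures in step 4 of the working apply only if it is wrong. The 0.90 baseline also assumes no drop-out; with 41 evaluable per arm the same formula gives Φ(0.30/√(0.4212/41) − 1.96) = Φ(1.00) = 0.84.

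Three things do not go away:

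- Granisetron and the spinal opioids are routine regimen, but metoclopramide for nausea fits the description of a drug that has to be given for comfort. The rescue reading is therefore not ruled out by the drugs everyone receives.
- Under the narrow reading, an additional antiemetic during surgery would still usually be given because of nausea.
- The sentence states an exclusion from the study that can operate intraoperatively. This is a rule the protocol sets, not a detail left to the SAP, and a criteria list could narrow the drugs covered without changing when this sentence applies.

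**Conclusion.** The concern holds. The protocol states an exclusion that can operate after randomisation and after treatment has begun, for reasons linked to the Objective 1 outcome, and its scope relative to the protocol's own rescue drug is not settled in the visible text.

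On the likely, narrow reading the total effect cannot be computed, because the number of such exclusions is not given. Each excluded IONV case moves the risk difference by 1.0 point (control) or 1.6 points (EA), in opposite directions. Three in one arm move it by 3.1 or 5.1 points. On the less likely reading that includes rescue, the loss could reach 37% of patients with no IONV events left; if half of the cases were excluded, power would be about 68% instead of about 90%.

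These figures rest on the protocol's planning rates, 49 per arm and a two-sided test. Confidence is medium, because the criteria list is not visible. The point should be fixed; it does not show that outcome events will in fact be discarded.

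**What to change.** Reconcile the exclusion sentence and the rescue sentence in the Study protocol section with each other and with the inclusion, exclusion and withdrawal criteria. Then state that:

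1. This exclusion applies only before randomisation.
2. Every randomised patient who receives an antiemetic or a supplementary opioid during surgery is followed to 24 hours and analysed in her assigned arm.
3. An intraoperative episode of nausea or vomiting that led to rescue counts as an IONV event.

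The rescue treatment itself does not change. The cost is one or two sentences by amendment. The small downside is that some analysed patients will have had an extra antiemetic or opioid, which a sensitivity analysis can address.

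### Does sizing the trial against granisetron alone undermine the stated 80% power when the randomised control also receives sham needling?

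*Protocol*

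**What the plan says.** Under Sampling Method, patients are randomised to electroacupuncture or sham. The sham group "shall receive 1mg of IV granisetron and sham acupuncture while the EA group shall receive 1mg of IV granisetron and electroacupuncture". The section headed Study protocol describes the sham as needles placed bilaterally at non-acupoints, with "superficial skin piercing (adequate depth to let patient feels needle is inserted", and with electrodes attached but no current. It also calls this the sham or placebo group.

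The Sample Size section names the control differently. Objective 1 says "37 control (granisetron alone) subjects will be needed" and gives as its basis "Prior data indicate that the failure rate among controls is 0.52", with 0.22 for the experimental arm. Objective 2 asks for "41 experimental (electroacupuncture+granisetron) subjects and 41 control (granisetron alone) subjects". Its rates come from a randomised trial reported as "43% in ondansetron group versus 16% in acupuncture plus ondansetron", and they are carried over to granisetron on this ground: "Since most of the literature stated the 5HT3 antagonist drugs (4mg IV ondansetron and 1mg IV granisetron) have similar efficacy to prevent PONV". Objective 2 gives the larger requirement: with the dropout allowance, "the sample size needed for this study is 98 patients", 49 per arm. Neither sample-size paragraph mentions sham.

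**The concern.** Read literally, the power statement refers to a comparator that no patient in this trial receives. Skin-piercing sham needling might have some effect of its own on nausea and vomiting. If it did, the control rate could be lower than under the drug alone, and the planned difference would shrink.

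The authors argued for one step from the cited trial to their own, the change of drug, and said nothing about the other visible step, the addition of sham needling. For Objective 1 the shown text names no source, so a reader cannot tell whether 52% came from a sham-treated control.

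Objective 2 is sized to just 80%, so any fall in the control rate with the electroacupuncture rate unchanged takes power below target. At stake is whether 98 patients are enough for the comparison that is actually randomised.

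**Working it through.** **Inputs (Protocol, Sample Size).** Objective 1: control 0.52, electroacupuncture 0.22, 37 per arm. Objective 2: control 0.43, electroacupuncture 0.16, 41 per arm, 49 after the dropout allowance. Type I error 0.05, power 0.80. Sidedness is not stated; two-sided reproduces the figures.

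**1. Reproducing the plan.** Formula for two proportions, unpooled variance:

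n = (1.960 + 0.8416)² × [p1(1−p1) + p2(1−p2)] / (p1−p2)², where (1.960 + 0.8416)² = 7.849.

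- Objective 1: 7.849 × (0.2496 + 0.1716) / 0.30² = 7.849 × 0.4212 / 0.0900 = 36.73, so 37.
- Objective 2: 7.849 × (0.2451 + 0.1344) / 0.27² = 7.849 × 0.3795 / 0.0729 = 40.86, so 41.

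Both match. A pooled-variance formula would give 40 and 44; the difference is one of method and has nothing to do with sham.

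**2. Power at the planned rates.** Power = Φ{(p1−p2) / √([p1(1−p1) + p2(1−p2)]/n) − 1.960}.

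| Per arm evaluable | Objective 1 | Objective 2 |
|---|---|---|
| 37 | 80.3% | – |
| 41 | 84.1% | 80.1% |
| 49 (all randomised) | 89.9% | 86.6% |

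**3. If sham lowers the control rate.** The protocol gives no rate that would show a sham effect, so the size must be assumed. Let sham produce a share f of the planned difference, with the electroacupuncture rate held: control rate = p1 − f(p1−p2).

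| f (assumed) | Obj. 2 control rate | Power, 41 / 49 per arm | Obj. 1 control rate | Power, 41 / 49 per arm |
|---|---|---|---|---|
| 10% | 40.3% | 72% / 79% | 49.0% | 76% / 83% |
| 25% | 36.25% | 57% / 65% | 44.5% | 61% / 68% |

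The lowest control rates that keep 80% power are 43.0% (Objective 2) and 50.4% (Objective 1) at 41 per arm, and 40.5% and 48.0% at 49 per arm.

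**4. How far step 3 depends on holding the electroacupuncture rate fixed.** If both Objective 2 rates fall by 2.7 points, to 40.3% and 13.3%, the difference stays at 27 points, the variance shrinks, and power at 41 per arm is 83%. At the 25% share, 80% is regained if the electroacupuncture rate is 11.1% rather than 16% (Objective 2) or 17.2% rather than 22% (Objective 1).

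**5. What the protocol shows about the missing input.** It reports no event rate for drug plus sham set against drug alone, so it gives no evidence that sham lowers either rate. It also does not say whether the cited trial's control patients, or those behind the 52%, received a sham. If they did, the rates carry over directly and only the label is loose.

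**The case for a change.** The strongest case for a change is that this is a contradiction within one document, so a separate analysis plan would not be expected to cure it. The authors evidently saw that their source differed from their trial, since they defended the change of drug, yet they left the sham unaddressed. The repair would be a few words and one sentence, with no added patients. Objective 2 has no reserve at 41 per arm, so a 3-point fall in the control rate, to 40%, would bring power to 71%.

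The first part stands: the label is wrong as written, and the assumption is not spelled out. The rest carries less weight. Any calculation sized to exactly 80% loses power when the control rate drops and the other rate is held, so the lack of reserve says nothing particular about sham. It is also too strong to say that readers cannot tell which control rate the power depends on: the protocol gives 52% and 43% as the rates expected in this study, and there is only one control arm to which they can apply. The absent source for 52% is weak evidence too, because the text shown has no background section and may not be the whole protocol.

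**Conclusion.** No change to the plan is needed. The sample-size paragraphs use a shorthand that names the active drug and omits the sham, while the sections that govern what patients receive are explicit. A statistician reading the whole protocol would take 43% and 52% as the assumed rates in the granisetron-plus-sham arm, and at those rates 37 and 41 per arm are correctly derived by the unpooled two-sided formula.

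The lower powers, 57% to 76% at 41 per arm, rest on two assumptions from outside the protocol: that sham yields 10% or 25% of the planned difference, and that the electroacupuncture rate does not move with it. Nothing in the protocol supports either, so the stated 80% is not shown to be wrong. Tidying the label and writing the assumption down would make the text clearer, but would leave the 98 patients, the allocation, the test, the endpoints and the conclusions as they are. The view would change only with evidence that the cited controls had no sham and that this kind of sham lowers nausea and vomiting; the protocol contains neither.
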